## 12.0 Study Design/Procedures

### Directions:

- 1) **Describe the overall study design (e.g.: single visit, single-blind, double-blind, non-randomized, randomized, blood draw, investigational drug, device etc.).**
- 2) **Provide a description of all study-related research procedures being performed, including the length of time involved.**
- 3) **Include procedures being performed to monitor research participants for safety or minimize risks.**
- 4) **Describe the source records including medical or educational records, which will be used to collect data about subjects.**
- 5) **Include a description of any device being used to collect data (e.g., eye tracker, step counter). If the device itself is being studied, include additional information in Section 29.**

1. The study follows a randomized controlled trial with a delayed intervention control design. The immediate cooking class group will receive their intervention in week 3 of the study, and the delayed cooking class group will receive their intervention in week 13 of the study.

2. *Baseline assessment meeting:* Regardless of randomized group, all participants will attend this meeting in week 1. Participants will come to a branch of the Cleveland Public Library to sign their consent form and complete the survey portion of their baseline assessment, consisting of Percieved Stress Scale, USDA Food Security Screener, and the Food Literacy, Environment, and Waste (FLEW) assessment which will be conducted via Qualtrics on tablets provided by the researchers. Two aspects of the baseline evaluation will be conducted after the baseline meeting: a) a series of two 24-hour dietary recalls (via phone calls) lasting approximately 30 minutes each and b) participants will be asked to weigh and log their food waste for one week. During the baseline assessment meeting, participants will be asked to share their phone number and participants will be given a kitchen food scale and waste log. They will be asked to return the log on the first day of class. Additionally, participants will be told what they can expect to happen at each Nourish class and will be coached on how to sign up for GroupMe to receive out-of-class information about Nourish. The duration of the baseline assessment meeting will be

approximately 60 minutes, and will occur two weeks before the immediate cooking classes group's 8-week Nourish class sessions begin.

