*Weekly Nourish classes:* Each Nourish class will last 90 minutes, and will run for 8 consecutive weeks, with one class per week. The immediate cooking class group will receive the Nourish classes in weeks 3-10, and the delayed intervention group will commence the Nourish intervention in weeks 13-20 (after the second intervention assessment period is complete).

Nourish will be held in the teaching kitchen at Dave's Market or CornUcopia. Each class will involve brief instructional video clips, hands-on cooking and tasting experiences. Participants will work individually and as part of small groups during instructional sessions. At the end of each class, participants will receive a grocery bundle and a kitchen gadget that serves both as an incentive and implementation support to promote improved cooking frequency and confidence. Participants will be asked to post photos of what they made with their groceries to the GroupMe, and we will encourage them to engage with fellow classmates on the GroupMe to encourage social support of cooking. Participants will earn raffle tickets for each time they post to the GroupMe and attend a class. A raffle drawing for a pressure cooker will be done at the second-assessment meeting (week 12) for the immediate cooking class group and at the last Nourish class for the delayed group (week 20).

The delayed intervention group will commence the Nourish intervention after the post-intervention assessment period is complete (in weeks 13-20).

A research assistant will attend each class to observe time use and lesson objectives covered.

*Second assessment meeting:* Participants will come to a branch of the Cleveland Public Library to complete their post assessment, consisting of PSS, USDA Food Security Screener, and the FLEW, as well as their return food waste log. Additionally, participants will be encouraged to enroll in an optional focus group series to provide feedback on Nourish. The duration of the second-assessment meeting will be approximately 35 minutes, and will occur in Week 12.

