## 16.0 Online Data Collection

- We will not collect data through an online platform.

1. List the online platform to be used. The preferred platforms are REDCap and Qualtrics, as these provide good data security and have options for collecting data without individually identifiable information.  
 The weekly post-class surveys, baseline and post intervention assessments will all utilize the platform Qualtrics. The two focus groups will be conducted via CWRU Zoom. Participants can join either via mobile phone or computer. REDCap will be used to schedule participant dietary recall interview in order to keep phone numbers secure.
2. If your intent is to collect the data without identifiers linked to an individual (including IP addresses), describe how you will ensure that no identifiable information will be associated with the data.
  - Qualtrics: enable Anonymize Responses setting (removes IP addresses and location data)
  - REDCap: use of the Public Survey Link
  - REDCap: use of a Participant List without a Participant Identifier field  
(Note: this does maintain a connection between the data and the individual, but it is only accessible to REDCap support personnel and not the researchers. Data collected in this manner should not be referred to as anonymous, but rather as data that is deidentified to the researchers).

Other: REDCap will be used internally to record participant phone numbers and dietary recall information

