## 20.0 Risks to Research Participants

1. List the reasonably foreseeable risks such as breach of confidentiality, discomforts, hazards, or inconveniences to the research participants related to their participation in the research. Include a description of the probability, magnitude, duration, and reversibility of the risks. Include the physical psychological, social, legal, and economic risks.  
DO NOT REPLY WITH “NO RISKS” For example, loss of privacy, boredom, emotional distress, etc.

Participation in the Nourish Pilot may result in participant inconveniences due to the requirement to travel to the meeting location for baseline/first and second assessments and for each in-person class. There is a low probability that the social aspect of the class setting may result in social risks, including embarrassment and frustration. The baseline/first and second assessments may cause some participant emotional distress due to topics of mindless eating and food waste. There is a low probability that participation in the codesign focus groups may result in discomforts and social risks, including

\* FERPA language: 1. Specify the educational records that may be both accessed and used in the research. 2. State the purpose of the access and use of records. 3. Identify to whom the records disclosure may be made.

embarrassment, frustration, or anger. It is anticipated that these risks are reversible and will, thus, not extend beyond the duration of each step in the study design, including not extending beyond class time, the duration of the assessments, and the duration of the focus groups. The magnitude of these risks is low due to minimal probability and severity.

2. If applicable, indicate which experimental procedures may have risks to the research participants that are currently unforeseeable. [Click here to enter text.](#)  
 N/A
3. If applicable, describe the risks to others who are not research participants. [Click here to enter text.](#)  
 N/A
4. Describe the availability of medical or psychological resources that research participants might need. [Click here to enter text.](#)  
 N/A

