## 23.0 Withdrawal of Research Participants

**Under what circumstance(s) would you withdraw a research participant from the research without their consent? (Check all that apply)**

- Safety Reasons; please explain [Click here to enter text.](#)
- Not following study instructions
- Being suspected of being a bot or bad actor (online surveys only)
- Other; please explain If a participant's eligibility criteria changes, in that they are no longer able to attend in-person classes or in-person assessments.
- N/A; please explain [Click here to enter text.](#)
- None

**Describe any procedures when a research participant withdraws or are withdrawn from the research, including partial withdrawal from procedures with continued data collection.**

If a participant withdraws or is withdrawn from the study, their associated data and identifiers will be removed from the dataset and destroyed within 30 days of the participant providing notice to the research team. If a participant withdraws but has already submitted some class assessment surveys, these will remain as part of the dataset due to the anonymous nature. Pre-assessment data will not be retained.

- N/A

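### Participants no longer able to attend in-person assessments can be withdrawn and their data destroyed, and the week-12 assessment has no remote or make-up route, so avoidable outcome data are lost

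*Combined protocol and SAP*

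**What the plan says.** **Week-12 assessment.** Under the second assessment meeting, Section 12.0 states: "Participants will come to a branch of the Cleveland Public Library to complete their post assessment". The Perceived Stress Scale, the USDA food security screener and the FLEW are completed there and the food-waste log is handed in. The meeting falls in week 12. Neither this section nor any other gives a window, a second date or a remote option.

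**Withdrawal.** Section 23.0 lists, among the reasons for withdrawing someone without their consent, a change in eligibility such that "they are no longer able to attend in-person classes or in-person assessments". On withdrawal, "their associated data and identifiers will be removed from the dataset and destroyed within 30 days", and "Pre-assessment data will not be retained". Only class surveys already submitted stay, because they are anonymous.

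**How the outcomes are collected.** Section 16.0 states: "The weekly post-class surveys, baseline and post intervention assessments will all utilize the platform Qualtrics". Section 12.0 says that the weekly surveys are filled in online. It describes the baseline recalls as "a series of two 24-hour dietary recalls (via phone calls) lasting approximately 30 minutes each", and has participants weigh and record their own waste for a week.

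**Use of the data.** Section 17.0 judges retention by how many participants stay until the post-intervention assessments are complete. It compares the arms by analysis of covariance, adjusting each outcome for its baseline value.

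**Travel.** Section 20.0 (Risks to Research Participants) names as an inconvenience the "requirement to travel to the meeting location for baseline/first and second assessments", and Section 25.0 leaves transport costs with participants.

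**The concern.** Aim 2 asks whether the retention and evaluation methods are feasible. As written, a difficulty in reaching the library can become a missing outcome, a person counted as not retained and, where the inability lasts, an erased record. The instruments themselves appear to need little or no attendance.

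Three things are at stake. First, the retention figure mixes willingness to continue with ability to travel, so it could understate what the same instruments would achieve with a remote option. Second, people who cannot travel may differ in food security or stress, which are two of the outcomes; a complete-case comparison could then be biased. Third, once the baseline of a withdrawn participant is destroyed, the team cannot compare those lost with those who stayed, so the pilot could not examine the second problem.

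**Working it through.** The plan states no dropout rate, power, effect size or standard deviation. The only figure to reproduce is the sample: 20 immediate + 20 delayed = 40 (Section 5.0), which adds up.

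**Step 1: what is lost, case by case.** Section 17.0 names five outcome variables: food waste, FLEW score, food security, perceived stress and diet quality.

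| Situation in week 12 | Withdrawn under Section 23.0? | Outcomes lost | Baseline kept? | Counted as retained? |
|---|---|---|---|---|
| Misses the one meeting but can still attend in general | Not expressly | 4 of 5 (three surveys and the log); recalls can still be done by telephone | Yes | No |
| No longer able to attend in-person assessments | Yes | 5 of 5 | No | No |

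In the first row the loss comes from the single mode of assessment. In the second, the withdrawal rule adds the loss of the recalls and the baseline. The two causes should be kept apart.

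**Step 2: what could be collected without attendance.**
- Surveys: on Qualtrics, the platform participants already use online each week. A link would be needed.
- Recalls: by telephone. The protocol says so for the baseline pair; Section 15.0 lists four per participant, and Section 16.0 schedules recalls through REDCap to protect telephone numbers.
- Waste log: kept by the participant for a week. Only its return is tied to the meeting.

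**Step 3: size.** One loss is 1/20 = 5% of an arm and 1/40 = 2.5% of the sample. The table illustrates larger losses. Assumptions, none from the documents: 0 to 8 of 40 lost for this reason alone, equally from both arms; two-sided 5% level; 80% power; baseline-to-follow-up correlation r = 0.5.

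Standard error in SD units = √[(1 − r²)(1/n₁ + 1/n₂)]. With 20 per arm this is √(0.75 × 0.10) = 0.274; with 16 per arm, √(0.75 × 0.125) = 0.306; ratio 1.118. The detectable difference uses the noncentral t with n₁ + n₂ − 3 degrees of freedom. Retention intervals are exact (Clopper-Pearson).

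| Lost of 40 | Per arm | Retention (95% CI) | SE ratio | Detectable difference (SD) |
|---|---|---|---|---|
| 0 | 20 | 100% (91.2–100) | 1.000 | 0.79 |
| 2 | 19 | 95.0% (83.1–99.4) | 1.026 | 0.81 |
| 4 | 18 | 90.0% (76.3–97.2) | 1.054 | 0.83 |
| 6 | 17 | 85.0% (70.2–94.3) | 1.085 | 0.86 |
| 8 | 16 | 80.0% (64.4–90.9) | 1.118 | 0.89 |

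From 0 to 8 lost, the detectable difference runs from 0.91 to 1.02 SD with r = 0 and from 0.65 to 0.73 SD with r = 0.7. The cost in precision is modest. The retention figure and possible bias matter more.

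**The case against.** The strongest reply is that Section 23.0 describes a lasting change in eligibility. A reader might infer that someone who attends all eight classes and then misses week 12 is withdrawn. The text does not say that, and the point does not rest on it.

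A reader might also infer that no outcome needs a visit. That goes too far. The baseline surveys are done on study tablets at the library, the second log is handed in at the meeting, and no passage says that the outcome scales may be completed unsupervised. The weekly online surveys are class feedback, so they show only that participants can use the platform. This stands as a caveat and is why mode must be recorded.

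Nor do the documents support saying that the withdrawal rule by itself caps retention at some percentage. They give no loss rate, and anyone who misses the only meeting lacks the survey with or without that rule.

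The plan also supports attendance: $125 for the post-class assessment set (Section 26.0), free parking (Section 25.0) and recruitment near the meeting places (Section 8.0). These may keep losses small, and no data in the documents show that losses would depend on food security or stress.

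The meeting has other uses: focus-group consent, focus-group enrolment and the immediate group's raffle. These are reasons to keep it. They do not require the outcome data to depend on it, since the focus groups are online and the invitation letters are handed out at classes 7 and 8.

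Finally, in-person attendance is a legitimate feasibility result under Aim 2. That is correct, and it can be reported without discarding the other data.

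**Conclusion.** The concern holds in a limited form. The protocol permits withdrawal, with destruction of data including the baseline, of someone no longer able to attend in-person assessments. It offers no other route at week 12 for anyone who cannot come. A single missed meeting costs four of the five outcomes and retained status; withdrawal costs all five and the baseline. Most of this appears avoidable with tools the study already has.

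The firm size is 5% of an arm per person. Any total is an assumption: under the illustration above, 2 to 8 losses would put measured retention at 95% to 80% and raise the standard error by 3% to 12%. A link with food security or stress is plausible because participants bear the transport cost, but it is not demonstrated.

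Two readings are assumed. The completed text beside the 'Other' option in Section 23.0 is taken as selected, because tick marks are not visible in the available text. The week-12 recalls are taken to be by telephone, as at baseline.

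**What to change.** 1. **Section 12.0, second assessment meeting.** Add that a participant who cannot attend in week 12 is sent a link to the same Qualtrics survey, to complete within that week, and returns the waste log by photo or mail. Telephone recalls proceed as planned.
2. **Section 23.0.** Remove inability to attend in-person assessments from the withdrawal reasons. State that data already collected from such participants are kept unless they ask for removal.
3. **Section 17.0.** Record the mode of each week-12 assessment. Report retention twice: overall, and in person only, so that attendance remains a feasibility result. Repeat the survey-outcome comparisons restricted to in-person completers as a sensitivity check, and tabulate mode by arm.

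**Cost.** This is a wording amendment, and the consent form must agree with the new rule on keeping data. Qualtrics and the telephone recalls are already in place. The downside is that a few follow-up surveys will be completed without staff present after a baseline done on study tablets, possibly in different proportions by arm. With few remote completers the sensitivity check will be descriptive. The separate trigger for inability to attend classes is not changed by this amendment.

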**E.g., "We will enroll 25 subjects at CWRU and plan to enroll 150 subjects study wide."**

The target sample for Nourish is 40 participants. Twenty participants will receive the intervention immediately. An additional 20 participants will be in the delayed intervention control group. The upper limit is also 40 due to space constraints and small-group educational activities. This is not a multi-site study.

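### The follow-up food-waste log has no stated issue date or logging week, and the baseline log is due back from controls in week 13, after the week-12 second assessment

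*Combined protocol and SAP*

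**What the plan says.** Section 12 describes the baseline log fully. At the week-1 meeting, which both arms attend, "participants will be given a kitchen food scale and waste log". Afterwards "participants will be asked to weigh and log their food waste for one week", and "They will be asked to return the log on the first day of class".

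The class calendar differs by arm. "The immediate cooking class group will receive the Nourish classes in weeks 3-10". The delayed arm has its classes in weeks 13 to 20, after the second assessment is finished. On that assessment the protocol states: "The duration of the second-assessment meeting will be approximately 35 minutes, and will occur in Week 12". The tasks listed for it are the stress, food-security and FLEW instruments, "as well as their return food waste log".

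Other sections show that waste is meant to be measured twice:
- Section 12, item 4 lists the waste log among the tools used both before and after the curriculum.
- Section 15 refers to waste logs in the plural.
- Section 26 pays $125 for a set of tasks that includes waste tracking at each of two times.
- Section 17 makes food-waste volume one of the ANCOVA outcomes, adjusted for the pre-treatment value of the same variable.

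**The concern.** For the baseline log, Section 12 gives the issue point, the duration and the return point. For the follow-up log it gives at most a return point, in a garbled phrase that does not say which log is meant. The return rule for the baseline log is tied to an event that falls ten weeks later in one arm than in the other.

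The randomised comparison of waste needs a baseline and a follow-up value from each participant, collected in the same way in both arms. With 20 per arm, few losses can be absorbed. If logs are missing because none was issued, or because two periods were confused, the pilot also learns less about whether the waste log is a workable measure. Feasibility of the evaluation methods is one of its stated aims (Section 2).

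**Working it through.** **Inputs.** Section 5: 40 participants, 20 immediate, and "An additional 20 participants will be in the delayed intervention control group". Section 12: the week numbers quoted above. The plan states no power, effect size, SD, dropout or missing-data rate, so it has no figure to reproduce.

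**Step 1: the calendar by arm.**

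| Item | Immediate | Delayed control |
|---|---|---|
| Baseline log issued | week 1 | week 1 |
| Baseline log due (first class) | week 3 | week 13 |
| Time from issue to return | 3 − 1 = 2 weeks | 13 − 1 = 12 weeks |
| Return relative to the week-12 assessment | 12 − 3 = 9 weeks before | 13 − 12 = 1 week after |
| Classes before week 12 | 10 − 3 + 1 = 8 | 0 |
| Last in-person session before week 12 | week 10 (2 weeks earlier) | week 1 (11 weeks earlier) |

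On a literal reading, controls at week 12 still hold the baseline log. If they hand in a log then, it may be the baseline one. If it is recorded as follow-up, the outcome is a value from around weeks 1 to 2 and there is no baseline covariate.

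**Step 2: ways to fill the gap in the follow-up log.**
- *Completed log returned at week 12.* It must be issued and started earlier. The immediate arm could receive it at a class. Controls have no in-person session at which to receive it.
- *Log issued at week 12.* The controls' logging week then runs up to or into their own classes, which start in week 13. The immediate arm has no later in-person point at which to return it, because its focus groups are online and optional.

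Either way, one arm lacks a described hand-off. The payment text does not settle the matter: the follow-up $125 is tied to tasks done once the classes have ended, which for controls literally means after week 20.

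**Step 3: what loss in one arm would cost (illustration only).** Assumptions, none from the documents: two-sided alpha 0.05, 80% power, SD = 1, baseline-to-follow-up correlation ρ from 0 to 0.7, no loss in the immediate arm, and control loss of 0, 25% or 50%. A participant without both values is taken to drop out of the ANCOVA.

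Detectable difference = (1.960 + 0.842) × √(1/n₁ + 1/n₂) × √(1 − ρ²)

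| n (immediate v control) | ρ = 0 | ρ = 0.5 | ρ = 0.7 | Power for 0.8 SD, ρ = 0 |
|---|---|---|---|---|
| 20 v 20 | 0.89 | 0.77 | 0.63 | 72% |
| 20 v 15 | 0.96 | 0.83 | 0.68 | 65% |
| 20 v 10 | 1.09 | 0.94 | 0.77 | 54% |

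For example, 20 v 10 at ρ = 0 gives 2.802 × √(0.05 + 0.10) = 2.802 × 0.387 = 1.09 SD.

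Loss may also bias the comparison. If a fraction m of controls is missing and they differ from the observed controls by d SD, the observed control mean is off by m × d. This runs from 0.10 × 0.25 = 0.025 SD to 0.50 × 0.50 = 0.25 SD.

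**The case against.** The strongest reply is that this is a feasibility pilot with five outcome areas in the ANCOVA plan and no declared primary. On paper the missing issue step applies to both arms alike, and no text says that classes will be used to hand out or prompt the log. The data-collection tools are separate attachments, so the log sheet may itself cover two periods. The follow-up payment makes no distinction between arms. All of this stands, and it limits the point to a risk rather than a demonstrated loss. It does not remove the week-13 return rule, which is in the text.

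Four stronger readings are tempting but not supported:
- *Controls have no contact after baseline.* They have two recall calls after the week-1 meeting, and the total of four recalls in Section 15 implies two more, at dates not given. All participants are coached on signing up to GroupMe. What controls lack is an in-person session between weeks 1 and 12.
- *Follow-up waste data will be missing mainly in controls.* The documents give no missingness rate for either arm. Neither the size nor the direction of a difference can be derived.
- *Controls will reach week 12 with no log.* As written, they still hold the baseline log, so confusion of periods is the firmer risk.
- *The pilot would declare the waste log infeasible.* Section 17 judges feasibility on numbers recruited and retained and sets no log-completion criterion.

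**Conclusion.** The point holds as a defect in the schedule. The protocol describes one issue of the waste log, its return rule falls after the second assessment for controls, and the intended follow-up log has no issue step or logging week in either arm. The ANCOVA outcome and its baseline covariate are therefore both open to loss, mislabelling or collection over different weeks by arm.

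How much this matters cannot be computed from the documents; the figures above show only what assumed control losses would do. The conclusion rests on two readings. First, the singular wording at week 1 is taken to mean one log for one period. Second, week 12 is taken as the follow-up point for controls, which agrees with two questionnaire rounds per participant in Section 15 and with their classes starting only afterwards. The point goes beyond missing operational detail because the written rule treats the arms differently, and it should be corrected before enrolment.

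**What to change.** Amend Section 12 as follows:
1. Give every participant two logs at week 1, each labelled by period, or mail the second log to both arms on the same day.
2. Replace the first-class return rule for the baseline log with one return point common to both arms, before the immediate arm's first class or soon after, for example by mail or photo.
3. Fix the same seven follow-up days, ending before the week-12 meeting, for both arms.
4. Send both arms identical reminders on the same dates, using the phone numbers already held.
5. In Section 17, report completeness of each log by arm.

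The follow-up payment wording in Section 26 should be brought into line, so that controls' week-12 tasks are clearly covered.

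The cost is protocol wording, 40 extra sheets, some postage and a few texts per participant. A log issued at week 1 for use about ten weeks later may be misplaced. Mailing it avoids that but needs a postal address for each participant.
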